Rationale: Standard groin treatment in recurrent vulvar cancer consists of a uni or bilateral inguinal lymph node dissection (IFL), whereas in the primary setting a sentinel lymph node (SLN) procedure is performed in case of unifocal tumours < 4cm without suspicious groin lymph nodes at imaging. The advantages of SLN procedure over an IFL are obvious: the short and long term sequels such as wound healing problems, lymph cyst formation, recurrent erysipelas and lymph oedema are much less common after SLN procedure. In a national retrospective analysis we showed that SLN is feasible in selected recurrent vulvar cancer patients. This national prospective observational study aims to investigate the safety of such procedure.

Since little is known on the outcome of 1st recurrent vulvar cancer we also gather more information on women with a first recurrence, not eligible for the SLN procedure.

Objective: The primary objective is to investigate the safety of replacing complete IFL by the SLN procedure in patients with local recurrent vulvar squamous cell carcinoma without suspicious groin lymph nodes.

Study design: This is predominantly a prospective multicentre observational study on sentinel lymph node (SLN) procedure in women with local recurrent vulvar cancer. Besides it is an observational study on the treatment and outcome of women with a local recurrent vulvar cancer, not eligible for the SLN procedure.

Study population: Women with their first local recurrence of vulvar cancer, 18 years and older, fit for surgical treatment, who had previous groin treatment as part of the primary treatment: none, uni- or bilateral SLN procedure, or IFL and/or radiotherapy. Excluded are women with previous ipsilateral IFL and radiotherapy, or bilateral IFL and radiotherapy. Women that do not fulfil these criteria will be included in the observational arm.

Intervention: Surgical treatment consists of standard local treatment (wide local resection, vulvectomy) of the vulvar tumour combined with a uni- or bilateral SLN procedure.

Main study parameters/endpoints: Primary end point is the number of groin recurrences after SLN procedure. Secondary endpoints: success rate of the SLN procedure, surgical drawbacks, wound healing problems, long term sequela, and quality of life in women treated for a 1st recurrent vulvar cancer.

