5.1.2 Preoperative definition of planned surgery

Prior to surgery the gynaecologic oncologist has to state what groin surgery should be done; ipsi or bilateral groin treatment and what treatment should be done in case the SLN is not visible, or not found during surgery. This decision relates to the previous groin treatment and whether or not the tumour crosses the midline. (See figures planned surgery). All SLN shown by imaging should be removed, also contralateral nodes in lateral tumours, and nodes in groins previously treated with IFL or radiotherapy, unless stated otherwise prior to surgery. In the current (standard) treatment protocol (www.oncoline.nl) groin surgery is not performed in local recurrent vulvar cancer after a previous IFL. Women should have an IFL in case of technical problems (SLN does not appear on the scintigraphy, or cannot be retrieved at surgery). Women that do not consent for a full IFL in case of technical problems (SLN does not appear on the scintigraphy, or cannot be retrieved at surgery), are more likely to experience groin recurrences (post-priory 17%). When women do not consent for IFL this should be noted prior to surgery.

Figures flow charts planned surgery see addendum 2.

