10.2 Secondary study parameters/endpoints

Groin recurrence after IFL

When enough patients agree on the standard arm (Group A) we might be able to calculate the number of women who develop a groin recurrence within 24 months after a negative IFL procedure in 1st recurrent vulvar cancer.

This failure is calculated by:

Total number of women with groin recurrence in a groin after negative IFL procedure divided by the number of women with uni- or bilateral IFL procedure * 100%.

Feasibility of the SLN procedure in recurrent vulvar cancer.

This is the success rate of detection and retrieval of the sentinel node, both related to the number of women, as well as number of groins in whom the proposed SLN surgery is successfully performed. (Group B1-B2)

Prior to surgery the surgeon has to state what groin surgery should be done; ipsi or bilateral groin treatment and what treatment should be done in case the SLN is not visible, or not found during surgery (see section 5.1.2.).

Feasibility is calculated:

- in relation to participants / patients:

Total number of women with successful SLN procedure(s) as per preoperative defined protocol, divided by the number of women that undergo the SLN procedure * 100%

- per groins:

Total number of groins with successful SLN procedure (as per preoperative defined protocol), divided by the number of groins that should be treated with the SLN procedure * 100%

Unexpected SLN's

This consists of SLN's in groins previously treated with IFL and or radiotherapy and SLN's found at unpredicted place, beyond the border of the regular IFL treatment. (Group B1-B2)

- *SLN in groins previously treated with IFL and or radiotherapy*
 - calculation of unexpected SLN's after previous IFL and or radiotherapy of the groin;

Total number of successful SLN's procedures in groins after previous IFL or radiotherapy of the groin, divided by total number of groins in whom a SLN was retrieved *100%.

- *SLN found at unpredicted places*

Total number of SLN's found at unpredicted places (outside the region of IFL), divided by total number of groins treated *100%.

- *Involvement of unexpected SLN's*

Total number of tumour positive unexpected SLN's, divided by total number of unexpected SLN's *100%.

Tumour positive SLN's

- as absolute number, and in relation to participants / patients:

Total number of women with uni or bilateral tumour positive SLNs, divided by the number of women with a successful SLN procedure * 100%.

- per groins:

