10.3 Other study parameters

Surgical complications

i.e., incidence of wound infections, wound breakdown, lymph oedema (see adverse effect Appendix 2) per patient and as absolute number. In relation to the previous

history and groin surgery performed, including all surgically treated patients (Groups non SLN cohort and A – C), comparing SLN treated groins with IFL treated groins.

Technical challenges

Description of unintended lesion of vena saphena magna, bleeding etc., duration of surgery to retrieve SLN. In relation to the previous history and groin surgery performed, including all surgically treated patients (Groups non SLN cohort and A – C), comparing SLN treated groins with IFL treated groins.

Patient's preferences

Standard treatment is uni- or bilateral IFL. In this study patients are offered SLN, with IFL when the SLN is not detected or retrieved. Preference for treatment is asked and noted in the file. The treating physician will note patients' preference in the application form. Patients will receive the Decisional Conflict Scale (DCS) and Decision Regret Scale (DRS). questionnaires regarding their treatment choices. (Group A – C) Decisions and regret scales will be compared between the groups (A – C) and related to patient characteristics like age, previous treatment and outcome like tumour positive groins and complications.

USS in follow up (Groups B1 - B2)

- 1) The number of suspicious USS in the follow up of women with negative LKT and SLN: USS with FNA, divided by the number of USS performed *100%.
- 2) Sensitivity and specificity of USS (with FNA) in women with negative LKT and SLN.
- 3) Protocol violation (USS not performed in women with negative LKT and SLN) divided by number of USS required in accordance with protocol *100%.

When a local or regional recurrence is diagnosed FU for this outcome stops.

Additional analyses

For the primary and secondary outcomes (failure of SLN and IFL procedure, feasibility, unexpected nodes, patients preferences, USS) univariate analyses will be done including the following parameters: tumour size, location, infiltration depth, treatment interval 1st and 2nd tumour, previous groin treatment, and age. Variables associated with ($P < 0.20$) in univariate analysis will be included in a multivariate logistic regression model. In the multivariate logistic and cox regression analyses, we only accepted ten events per variable to avoid overfitting (19).

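### Unexpected sentinel nodes are defined partly by previous groin treatment and then regressed on it, so that association is built in by definition

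*Protocol*

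**What the plan says.** Section 10.2 (Unexpected SLN's) defines the outcome as a composite: "This consists of SLN's in groins previously treated with IFL and or radiotherapy and SLN's found at unpredicted place", the unpredicted place being beyond the regular IFL border. The two components have separate percentages with different denominators. The first is "divided by total number of groins in whom a SLN was retrieved". The second is "Total number of SLN's found at unpredicted places (outside the region of IFL), divided by total number of groins treated". The section then pools both components as the denominator for tumour involvement of unexpected SLNs, so the pooled term is the protocol's own usage.

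Section 10.3 (Additional analyses) lists the regression outcomes as "failure of SLN and IFL procedure, feasibility, unexpected nodes, patients preferences, USS". The candidate predictors for all of them are "tumour size, location, infiltration depth, treatment interval 1st and 2nd tumour, previous groin treatment, and age". Variables with P < 0.20 "in univariate analysis will be included in a multivariate logistic regression model", subject to ten events per variable. No predictor is excepted for any outcome, and no unit of analysis (SLN, groin or woman) is fixed.

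Previously treated groins do enter the SLN procedure. Section 5.1.2 includes among the SLNs to be removed "nodes in groins previously treated with IFL or radiotherapy, unless stated otherwise prior to surgery". The Summary gives the eligible groin histories as "none, uni- or bilateral SLN procedure, or IFL and/or radiotherapy".

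**The concern.** A predictor that forms part of the outcome's definition cannot be tested against that outcome. Every groin with earlier IFL or radiotherapy that yields an SLN is unexpected by rule. A groin without such treatment is unexpected only if the SLN lies outside the IFL region. A strong association would appear even if drainage had nothing to do with previous treatment.

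Three things follow:

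- The study could report as a finding a relation that it imposed. Aberrant drainage is part of the protocol's rationale (sections 1, 11.4 and 13.1), so readers would give such a result weight.
- Depending on the unit, the coefficient is either not estimable or finite and meaningless. The finite case may mislead more, because nothing in the output signals a problem.
- Events created by the definition count toward the ten-events-per-variable rule, yet say nothing about tumour size, location, depth, interval or age. The rule would then admit more covariates than the data support.

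**Working it through.** **The plan's own figures.** The protocol gives no figure for this regression. The inputs used for scale do reproduce: 150 / 0.618 = 242.7, so 243 women included. Women having the SLN procedure: 150 / 0.64 = 234.4. Women with a retrieved SLN: 0.75 × 234.4 = 175.8, about 176.

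**Inputs from section 1 (retrospective series).** SLNs outside the IFL border in 2 groins; 44 groins in all, with the procedure performed as planned in 84%, i.e. 0.84 × 44 = 37. The rate is 2/44 = 4.5% or 2/37 = 5.4%.

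**Assumptions (not in the documents).** Share of groins with previous IFL or radiotherapy: 10%, 20% or 30%. Groins with a retrieved SLN: 176 (one per woman, a minimum). Retrieval in treated groins: 84%, 75% or 60%.

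**(a) Unit: groin with a retrieved SLN (denominator of the first component).** The cell for treated and not unexpected is zero by construction.

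| Share treated | Treated: unexpected / not | Untreated: unexpected / not | Fisher p |
|---|---|---|---|
| 10% | 18 / 0 | 9 / 149 | 3e-18 |
| 20% | 35 / 0 | 8 / 133 | 1e-29 |
| 30% | 53 / 0 | 7 / 116 | 1e-37 |

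For the 20% row the logistic fit does not converge. The coefficient is 14.0 (SE 46) after 10 iterations and 24.8 (SE 10,012) after 20, which is quasi-complete separation. With the first component alone as outcome, the table is 35 / 0 versus 0 / 141: outcome and predictor coincide, and separation is complete.

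Passing the P < 0.20 screen here refers to an exact test. A Wald test taken from the unconverged fit would give z = 14.0 / 46 = 0.3, which is not a usable test.

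**(b) Unit: groin attempted, failed retrieval counted as not unexpected.** Take 210 groins, 42 treated (20%) and 168 untreated. Untreated events: 168 × 0.84 × 0.054 = 7.6, so 8 / 160.

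- Retrieval 84%: 35 / 7; OR = (35 × 160) / (7 × 8) = 100
- Retrieval 75%: 32 / 10; OR = (32 × 160) / (10 × 8) = 64
- Retrieval 60%: 25 / 17; OR = (25 × 160) / (17 × 8) = 29

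The fit converges, with SE about 0.5 on the log scale. All Fisher p-values are 1e-14 or smaller.

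**(c) Unit: woman.** This was simulated with SLN position independent of previous treatment: 176 women, 25% with one treated groin, 60% retrieval there, 5.4% outside the border, 2,000 runs. P < 0.20 occurred in every run, the median OR was about 28, and separation arose in 0.05% of runs.

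**Events per variable.** In the 20% row of (a) there are 35 + 8 = 43 events, which appears to allow four covariates. Thirty-five arise by definition; 8 carry information on the other predictors.

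**Events if only SLNs outside the IFL region are the outcome.** 176 × 2/44 = 8.0; 176 × 2/37 = 9.5; 250 × 2/44 = 11.4; 250 × 2/37 = 13.5. The 250 is an assumed upper figure. At ten events per variable, all four allow one covariate at most.

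**The case against.** The strongest reply has four parts.

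**Separate reporting.** Section 10.2 reports SLNs at unpredicted places with their own numerator and denominator, and calculates no pooled percentage of unexpected SLNs. The term in section 10.3 may be shorthand for two measures, and a statistical analysis plan could say which one enters each model. The separate reporting stands, so the descriptive result on drainage outside the IFL region is not lost. But the protocol fixes both the outcome and the predictor and makes no exception. Reading the term as two measures does not help either: regressing the first component alone on previous treatment gives complete separation.

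**Fitting the model.** A reader might infer that the logistic model cannot be fitted at all. The documents do not support this. The unit is not fixed, the second component uses groins treated as its denominator, and the Summary describes previous treatment by woman. With attempted groins or women as the unit, the model converges.

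**Other predictors.** A reader might also infer that they are lost. They are not. Under quasi-complete separation only the coefficient for previous IFL or radiotherapy diverges. The others are then estimated from the untreated groins, where the composite equals an SLN outside the IFL region. The contrast between no previous treatment and a previous SLN procedure is not part of the definition.

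**Weight and yield.** This is one predictor for one outcome among the additional analyses, and the cleaned outcome has few events. Both are true. They limit the importance of the point and the ambition of the remedy, but do not remove the overlap.

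**Conclusion.** The point holds in a limited form. As written, sections 10.2 and 10.3 build in an association between unexpected nodes and previous IFL or radiotherapy. By an exact test it passed the P < 0.20 screen in every scenario tried, including one in which SLN position was independent of previous treatment. The result is either a coefficient without a finite estimate (retrieved groins or SLNs as unit) or a large artefactual odds ratio (attempted groins or women as unit).

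The sizes rest on assumed numbers of groins, shares previously treated and retrieval rates. The direction does not, because it follows from the definition. The ten-events rule is also weakened, since most of the apparent events can be definitional. The primary endpoint, the sample size and the stopping rule are untouched. It should be corrected before analysis, but it does not threaten the trial's main conclusion.

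**What to change.** In section 10.3:

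- Restrict the regression outcome for unexpected nodes to SLNs outside the IFL region, state the unit of analysis, and keep previous groin treatment as a candidate predictor.
- Report SLNs found in previously treated groins descriptively only. Retrieval in relation to previous treatment is already covered by the per-groin feasibility outcome, which section 10.3 also regresses on previous groin treatment.
- State that about 8 to 11 events are expected (up to about 14 if 250 groins and 5.4% apply). The protocol's own ten-events rule then allows about one covariate, and the analysis is essentially univariable.

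The cost is two or three sentences. No new data are needed, because section 8.1.2 already records whether each SLN lay within the IFL region.

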4.3 Exclusion criteria

A potential subject who meets any of the following criteria should not undergo the SLN procedure in the study arm (A-B), the patient can be asked for the non SLN cohort.

- Inoperable tumours and tumours with diameter > 4 cm.
- Patients with inguinofemoral lymph nodes at palpation clinically suspect for metastases, at radiology enlarged (> 10 mm short axis) / suspicious groin nodes and with cytological proven inguinofemoral lymph node metastases.
- A history of bilateral IFL **and** radiotherapy to the groins.
- A lateral tumour and history of ipsilateral IFL **and** ipsilateral radiotherapy.
- Tumour encroaching urethra, vagina, or anus.
- Previous surgery of the vulva was not radical (margin < 1 mm) and additional treatment (2nd surgery or radiotherapy) was not performed.
- Multifocal recurrent disease of the vulva.
- Synchronous, non- curable 2nd malignancy.

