The overall survival and progression free survival for the different groups (non SLN cohort and Groups A – C) will be described using the Kaplan-Meier analysis. The overall survival (OS) is defined as the interval between the date of surgery for 1st recurrent vulvar cancer and the date of death or last visit/date last known to be alive. Progression Free Survival (PFS) is defined as the interval between the date of surgery for 1st recurrent vulvar cancer and the date of documented disease progression, or last follow-up. Groin recurrence is censored in case of a 3rd local (vulvar) recurrence since any groin recurrence after such an event cannot be related to the 1st or 2nd recurrence. If a patient is lost to follow-up or dead because of unknown reason, she will be censored as of the date of last contact for the PFS.

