11.4 Benefits and risks assessment, group relatedness

A full IFL is still the preferred treatment of recurrent vulvar cancer, but no comparison is made with SLN biopsy. However in breast cancer, repeat SLN is feasible and provides reliable results(12). There are no arguments why vulvar cancer should have different outcomes than breast cancer. It is possible that a SLN might increase the number of women with groin failure, opposed to standard IFL. However in our retrospective study, in 2 out of 27 patients, the SLN was located outside the surgical margins of the normal IFL, possibly due to an aberrant drainage pattern(11). So, the women with an aberrant pattern might benefit of the SLN procedure in case a positive SLN is found. Ultra-staging of the retrieved SLN might detect microscopic metastases that might have been unnoticed in IFL, and thereby improve the diagnostic (and may be clinical) outcome of affected women.

Since the majority of patients with recurrent vulvar cancer are frail, an observational study of accuracy, in which a SLN biopsy and an IFL are performed consecutively in one surgical procedure is not feasible: too many frail women will refuse this extensive surgery.

Since it is not guaranteed that a repeat SLN procedure is as safe as a primary SLN procedure, we have a stopping rule and a Safety Committee installed.

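### Protocol section 10.3 defines PFS without naming death as an event and censors deaths of unknown reason, so the curve overstates PFS; the surgery start date may also be missing for some women in the non-SLN cohort

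*Protocol*

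**What the plan says.** The definitions stand under Additional analyses in Protocol section 10.3.

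- **OS** is the time from surgery for the first recurrence "and the date of death or last visit/date last known to be alive".
- **PFS** has the same start, and its end is written as "and the date of documented disease progression, or last follow-up".
- **PFS censoring.** A woman lost to follow-up is handled in the same way as one who is "dead because of unknown reason, she will be censored as of the date of last contact for the PFS".
- **Groups.** OS and PFS "for the different groups (non SLN cohort and Groups A – C) will be described using the Kaplan-Meier analysis".

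Entry to the non-SLN cohort is described in several places:

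- The Summary includes fitness for surgery in its description of the study population, and sends women who do not meet that description to the observational arm.
- Section 3 first says that the centres register women who are fit for surgery. It then invites every woman with a first recurrence who is not eligible for the SLN procedure, with inability to read Dutch or English as the only stated exception.
- Section 4.2 lists fitness for surgery only among the conditions for the SLN procedure.
- Section 4.3 gives "Inoperable tumours and tumours with diameter > 4 cm" as a reason not to undergo the SLN procedure, and says such a woman can be approached for the non-SLN cohort.

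**The concern.** PFS is ordinarily read as the probability of being alive without progression. A woman who has died is no longer progression-free and alive, whatever the cause. If her death is censored, Kaplan-Meier treats her as someone who could still progress later and gives her the same future risk as the women still under observation. Some deaths of unknown reason may also be progression that nobody documented; these are counted as neither progression nor death.

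Death without documented progression is foreseeable here. Section 11.4 states: "Since the majority of patients with recurrent vulvar cancer are frail". Since the protocol does not say what to do with deaths of known cause, two analysts could also draw different PFS curves from the same data.

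The second issue is the start date. A woman who is not operated on has no date of surgery, so neither OS nor PFS can be computed for her as written. Section 13.2 says women are asked to join the non-SLN cohort in order to close a gap in knowledge about outcome, so it matters whom its curves describe.

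**Working it through.** **1. What happens to each kind of death under the text**

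| Outcome | OS | PFS |
|---|---|---|
| Documented progression | not an event | event |
| Death, unknown reason | event | censored at last contact (explicit) |
| Death, known cause, no documented progression | event | not addressed; by the letter of the definition, ends at last follow-up |
| Alive at last contact, no progression | censored | censored |

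The OS definition names death and the PFS definition beside it does not.

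**2. Direction of the error**

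Take one set of data and count an extra event in place of a censoring at the same time. The women at risk are the same, and the Kaplan-Meier factor at that time can only fall. If the censoring is placed at an earlier last contact, the numbers at risk differ briefly between that contact and the death, but once the death is counted the curve that includes it is again the lower one. So the curve with deaths censored overstates PFS wherever a death without documented progression has been censored.

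**3. Size (illustration only)**

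The protocol states no PFS rate or event count, so there is no figure of its own to reproduce. Assumptions: independent risks; 24-month progression P of 20-40%; 24-month death without documented progression D of 2-15%; all such deaths censored. The horizon of 24 months is that of the scheduled three-monthly follow-up in section 5.1.8.

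- PFS as written: 1 − P
- PFS counting death: (1 − P) × (1 − D)
- Overstatement: (1 − P) × D

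| P | D | As written | Counting death | Overstatement (points) |
|---|---|---|---|---|
| 20% | 2% | 80.0% | 0.80 × 0.98 = 78.4% | 1.6 |
| 20% | 15% | 80.0% | 0.80 × 0.85 = 68.0% | 12.0 |
| 30% | 2% | 70.0% | 0.70 × 0.98 = 68.6% | 1.4 |
| 30% | 5% | 70.0% | 0.70 × 0.95 = 66.5% | 3.5 |
| 30% | 10% | 70.0% | 0.70 × 0.90 = 63.0% | 7.0 |
| 30% | 15% | 70.0% | 0.70 × 0.85 = 59.5% | 10.5 |
| 40% | 2% | 60.0% | 0.60 × 0.98 = 58.8% | 1.2 |
| 40% | 15% | 60.0% | 0.60 × 0.85 = 51.0% | 9.0 |

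The range is 1.2 to 12.0 points. If deaths of known cause were counted as events, only the unknown-cause deaths would be censored. Writing 1 − D as S(known) × S(unknown), the overstatement becomes (1 − P) × S(known) × (1 − S(unknown)), which is never larger than the figure in the table.

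**4. Start date**

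The Summary, the invitation in section 3 and section 4.3 all allow a woman who is unfit for surgery or has an inoperable tumour into the non-SLN cohort. The registration sentence in section 3 does not. Elsewhere in section 10.3 the analyses of complications and technical challenges are limited to surgically treated women; the survival paragraph has no such limit. Whether women without a surgery date exist in the data therefore depends on which of the conflicting sentences governs.

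**The case against.** **Deaths of known cause may have been meant as events.** A rule that censors only deaths of unknown reason would be oddly narrow if every death were censored, and section 9.3 monitors death of disease. This stands. A reader might infer that the protocol censors all deaths, but the text supports less: unknown-cause deaths are censored and known-cause deaths are left open. The defect survives either way, because unknown-cause deaths are still not counted and PFS would depend on attribution of cause.

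**Censored women are not discarded.** They contribute time at risk up to last contact. Correct; the error is in what is assumed about them afterwards.

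**Inoperable women may never enter.** Section 3 registers women fit for surgery, and section 13.2 describes the non-SLN cohort in terms of an IFL done for proven groin metastases. This stands as far as it goes, so the start-date issue is conditional. A reader might infer that the worst prognoses are being dropped from the non-SLN curves; the protocol gives no number of non-operated women and no rule that drops them.

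**No group is shown to be frailer.** A reader might infer that group C and the non-SLN cohort are the frailest and that comparisons between groups are distorted accordingly. Section 11.4 speaks of the patients as a whole, and group C is defined by refusal of groin surgery, not by frailty. That inference is not supported.

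**A separate SAP could settle this.** The protocol itself fixes the definition and the censoring rule, so this is not a detail merely left for later.

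**Conclusion.** The PFS definition is wrong as written. It does not name death, it censors deaths of unknown reason, and it is silent on deaths of known cause. The direction of the error is certain once any woman dies without documented progression and is censored. The size is not known from the protocol: about 1 to 12 points at 24 months under the assumed rates, and less if known-cause deaths are treated as events. Heavier assumed mortality gives larger gaps (25% progression and 20% death: 0.75 − 0.75 × 0.80 = 0.15, or 15 points), but nothing in the protocol supports choosing such rates.

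The start date is a separate defect, shared by OS. It does not cause the missing death event, and it has an effect only if non-operated women enter the non-SLN cohort, on which the protocol contradicts itself.

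Severity is minor. Both curves are descriptive additional analyses with no test or decision rule attached. OS counts death and is shown for the same groups, so mortality remains visible. The primary endpoint, the sample size and the stopping rule do not use PFS.

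**What to change.** 1. Define the PFS event as documented progression or death from any cause, whichever comes first, and censor only women alive and progression-free at last contact. If the sponsor wants time to progression instead, call it that and report cumulative incidence with death as a competing event.
2. Reconcile the Summary, section 3 and section 4.3 on whether women without surgery can enter the non-SLN cohort.
3. If they can, start OS and PFS in all groups at a date these women also have, such as registration, which section 12.1 places after consent and Appendix 4 before surgery. If they cannot, surgery can stay as the start date.

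The cost is a change of wording and one derivation. Deaths are already reported to the sponsor (section 9.2.2), and their causes are reviewed each year (section 9.3). The PFS curves will look slightly less favourable.
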